For **Aim 1 (infant age of egg introduction)**, we will first classify the infants based on their age of egg introduction: never, <2 m, 2-3 m, 4-5 m, 6-8 m, 9-11 m, and 12 m. Then we will compare their physical growth, obesity, cardio-metabolic risk profile, risk of food allergy, and cognition test scores in mid-childhood and adolescence using Chi-square tests (categorical outcomes) or ANOVA tests (continuous outcomes). We will fit multivariable linear (continuous outcomes) or logistic (binary outcomes) regression models with fractional polynomial functions of infant age of egg introduction, adjusted for significant confounders. Both linear (e.g., earlier introduction, high probability of the outcome) and non-linear (e.g., threshold effect) associations will be tested. The non-linear trend will be examined through visualization of scatter plots and statistical tests of polynomial term of infant age of egg introduction in the regression models. If the polynomial terms of age are not significant, we will drop it and consider the association to be linear.

Then, we will fit a mixed effect model (SAS PROC MIXED) for continuous outcomes (height z-score and BMI z-score) and a generalized linear mixed effect model (SAS PROC GLIMMIX) for binary outcomes (obesity and diagnosis of food allergy) that were measured repeatedly across multiple age points. The mixed effect model will include random intercepts, random slopes for age effects, and autoregressive variance-covariance matrix across different time points. Independent variables in the model will include infant age of egg introduction, outcome age point (mid-childhood and adolescence), the 2-way interaction term (infant age of

egg introduction × outcome age point), and significant covariates. The 2-way interaction term quantifies the extent to which infant age of egg introduction can affect the specific outcome. The PI has experience with using mixed effect models for examine child growth measures and multiple publications in this area.^{51,52}

For **Aim 2 (frequency of infant egg intake)**, we will first classify the infants based on their frequency of egg intake: never, <once/week, once/week, 2–4 times/week, nearly daily or daily, and ≥ 2 times/day. Then, we will use similar analytic methods mentioned above for Aim 1 to compare their health and developmental outcomes.

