Statistical Power. We expect sufficient statistical power for our hypothesis-driven data analyses for both Aims, because 1) the 2 cohorts had relatively large sample sizes (N=2,128 for Project Viva and N=3,033 for IFPS II), which are sufficient to detect a small odds ratio (1.46 for Project Viva, 1.38 for IFPS II with type 1 error being 0.05 and power being 0.8) of binary child outcomes (e.g., food allergy) between infants with different egg consumption (e.g., egg introduced at ≥ 12 m vs 6-8 m) or a small effect (effect size=0.054 for Project Viva, 0.051 for IFPS II) of infant egg consumption on continuous outcomes (e.g., intelligence score); 2) most child outcomes were measured repeatedly; 3) infant egg consumption varied largely within cohorts.

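### The detectable effect sizes given for continuous outcomes fit only one-degree-of-freedom tests and do not cover the planned multi-group and non-linear tests

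*Combined protocol and SAP*

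**What the plan says.** Under Project Design, the Statistical Power paragraph expects adequate power for the analyses of both Aims. It rests this first on "relatively large sample sizes (N=2,128 for Project Viva and N=3,033 for IFPS II". For continuous outcomes the detectable effect is given as "a small effect (effect size=0.054 for Project Viva, 0.051 for IFPS II) of infant egg consumption on continuous outcomes", with an intelligence score as the example. The phrase "with type 1 error being 0.05 and power being 0.8" stands in the parenthesis on the odds ratios and is not repeated for the continuous outcomes. No metric (d, f, f-squared or r), test, degrees of freedom or sidedness is stated for 0.054 and 0.051.

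The Data analysis section, Aim 1, first compares outcomes "using Chi-square tests (categorical outcomes) or ANOVA tests (continuous outcomes") over seven age-of-introduction groups: "never, <2 m, 2-3 m, 4-5 m, 6-8 m, 9-11 m, and 12 m". Aim 2 applies similar methods to six frequency groups: "never, <once/week, once/week, 2–4 times/week, nearly daily or daily, and ≥ 2 times/day". Adjusted regressions with fractional polynomials follow. If the polynomial terms are not significant, they are dropped and the association is treated as linear.

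**The concern.** A detectable effect size belongs to a particular test. With the same N and the same effect, an omnibus test over six or seven groups, or a joint test of several curve terms, has less power than a test of one slope. The printed values are about as small as a single-slope test allows at these sample sizes, yet they are offered in support of all the analyses of both Aims.

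What is at stake is how a null result is read. Someone who takes 0.054 and 0.051 as the effects that each planned test can detect will overrate the sensitivity of the group comparisons and of the search for curvature. Curvature matters because the plan falls back to a straight line when polynomial terms are not significant: low power for those terms makes the fallback likelier even if the true relation is curved. A U-shaped relation can also have little linear correlation, so a single-slope figure says little about the chance of finding it.

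**Working it through.** **Inputs from the documents.** N = 2,128 (Project Viva) and 3,033 (IFPS II); printed effects 0.054 and 0.051; seven groups (6 df) and six groups (5 df).

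**Assumptions.** The effect is Cohen's f, which is practically equal to |r| at this size. There is one measurement per child and no loss from missing data. Alpha 0.05 and power 0.8 carry over from the odds ratios. The degree of the fractional polynomial is not stated; two terms tested jointly (2 df) is taken as the main case.

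**Step 1: reproduce the printed values.** For 1 df, detectable f = (z_alpha + z_power)/√N, with √2,128 = 46.13 and √3,033 = 55.07.

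| | One-sided: (1.645 + 0.842)/√N | Two-sided: (1.960 + 0.842)/√N | Printed |
|---|---|---|---|
| Project Viva | 0.0539 | 0.0607 | 0.054 |
| IFPS II | 0.0451 | 0.0509 | 0.051 |

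Each value is reproduced by a 1-df test, but with opposite sidedness, so no single convention gives both. The odds ratios do not settle which was meant. With an equal split of the cohort and an assumed base risk of 10%, 1.46 and 1.38 have two-sided power of 80.3% and 80.8%. A one-sided test would reach 80% at an assumed base risk between 6% and 8%.

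**Step 2: 1-df power at the printed values.** Power = Φ(f√N − z_alpha).
- Project Viva: 0.054 × 46.13 = 2.491. One-sided Φ(0.846) = 80.1%; two-sided Φ(0.531) = 70.2%.
- IFPS II: 0.051 × 55.07 = 2.809. Two-sided Φ(0.849) = 80.2%.

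**Step 3: the other planned tests.** Noncentral F with λ = N·f², numerator df as listed, denominator df = N − df − 1, alpha 0.05.
- λ for Project Viva = 2,128 × 0.054² = 6.21.
- λ for IFPS II = 3,033 × 0.051² = 7.89.

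| Test | df | Power at printed value, Viva / IFPS II | f for 80% power, Viva / IFPS II |
|---|---|---|---|
| One linear term | 1 | 70.2% / 80.2% | 0.061 / 0.051 |
| Two-term polynomial | 2 | 59.9% / 71.1% | 0.067 / 0.056 |
| Six-group ANOVA (Aim 2) | 5 | 44.6% / 55.7% | 0.078 / 0.065 |
| Seven-group ANOVA (Aim 1) | 6 | 41.5% / 52.3% | 0.080 / 0.067 |

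If the curve is charged a nominal 4 df, its power is 48.4% / 59.7%. Rounding of the printed effects moves any of these figures by about one point.

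**Step 4: split the shortfall.** For the seven-group ANOVA in Project Viva, power falls from 80.1% to 70.2% through sidedness (9.9 points), then to 41.5% through df (28.7 points). In IFPS II the whole fall, 80.2% to 52.3% (27.9 points), is df.

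**The case against.** Several points on the other side have force.

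- **The plan never promises 80% power for the ANOVAs.** This stands. The 0.8 is printed beside the odds ratios, the ANOVAs are unadjusted first comparisons, and a 1-df linear term is also planned. A reader might infer that the plan states 80% and delivers about half; the text does not say that. What remains is that the paragraph claims adequacy for both Aims while no continuous-outcome figure covers an omnibus or non-linear test.
- **The metric is undefined.** This also stands, so the power figures are conditional on f or |r|. Other readings do not rescue the values. As f-squared, power is essentially 100%, so they would not be 80% thresholds. As d between two equal halves, power is 24% and 29% even with 1 df.
- **A repeated-measures calculation could give such small values.** With λ = N·f²·m/(1 + (m − 1)ρ), six groups, m = 4 and ρ = 0.3 give 0.0777/√(4/1.9) = 0.0536 in Project Viva. Seven groups, m = 6 and ρ = 0.5 give 0.0671/√(6/3.5) = 0.0512 in IFPS II. The 1-df origin is therefore an inference that holds for single-measurement tests. But m and ρ here are invented: the documents give neither, and the power paragraph lists repeated measurement as a separate reason. The continuous mixed models are limited to height and BMI z-scores. The intelligence score used as the example is measured once with KBIT-II at 7 years, and with a different test at 3 years.
- **Hypotheses 2 and 3 are not shown to be underpowered.** A reader might infer that they are, because they predict non-linear relations. They concern the average probability of six binary outcomes from logistic models, so these figures do not bear on them directly. The point about curvature rests on the non-linear tests planned for continuous outcomes.

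**Conclusion.** Wrong as written, minor severity. Under the assumptions listed, 0.054 and 0.051 fit only 1-df tests, and not the same one: for a two-sided test the Project Viva value should be 0.061. They do not describe the seven-group ANOVA, the six-group ANOVA or a multi-term curve. For the seven-group ANOVA, the effect detectable with 80% power is 48% above the printed value in Project Viva (0.0801/0.054) and 32% above it in IFPS II (0.0671/0.051).

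The documents do not support the stronger conclusion that the study cannot detect small effects. Even f = 0.080 is about 0.64% of variance (0.0801²/(1 + 0.0801²)), so the qualitative claim survives at full N. Full N is the favourable case, since the plan itself expects missing exposures and outcomes and will impute them. Project Viva, where the intelligence score is measured, is the cohort more affected.

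**What to change.** In the Statistical Power paragraph:

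1. Name the metric, sidedness, test and degrees of freedom for the continuous outcomes, and say whether alpha 0.05 and power 0.8 apply to them.
2. Restate the two-sided 1-df detectable effect as 0.061 (Project Viva) and 0.051 (IFPS II), labelled as applying to a single linear term.
3. Add the detectable Cohen's f at 80% power for the other tests: 0.080 / 0.067 (seven-group ANOVA), 0.078 / 0.065 (six-group ANOVA) and 0.067 / 0.056 (two-term polynomial, or the value for whichever degree is chosen).
4. State that these assume full N and one measurement per child. If a repeated-measures calculation was used, give the number of measurements, the correlation and the outcomes it covers.

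This costs a few sentences and a short recalculation. No data or analyses change; the stated sensitivity becomes slightly less favourable.

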Hypotheses: The effects of infant age of egg introduction and frequency of egg intake will vary by the child outcome of interest (**Hypothesis 1**). We predict a non-linear association between age of egg introduction and the average probability of multiple child outcomes (i.e., stunting, underweight, obesity, high risk of metabolic syndrome, food allergy, and cognitive delay), with the optimal age being a time point that falls between 6-12 months (**Hypothesis 2**). We also predict a non-linear association between frequency of infant egg intake and the average probability of multiple child outcomes, with the optimal frequency being 2-4 times per week (**Hypothesis 3**).

3) Project Design:

Sample/Data. We propose a 2-year study to examine the extent to which two important aspects of infant egg consumption (i.e., age of introduction and frequency of intake) influence physical growth, obesity, cardio-metabolic health, risk of food allergy, and cognition development in mid-childhood and adolescence. Guided by a life course framework (**Figure 1**), we will use existing secondary data from two US longitudinal birth cohorts that tracked mother-child dyads from pregnancy to adolescence: 1) **Project Viva** (1999-present, N=2,128 newborns) that followed children at delivery, 6 months (m), 1 year (y), 2 y, 3 y, 4 y, 5 y, 6 y, 7 y, 8 y, 9 y, 10 y, 11 y, 12-13 y, 14 y, and 15 y of child age,³⁷ and 2) **Infant Feeding Practices Study II** (IFPS II, 2005-2012, N=3,033 newborns) that followed children at neonatal (1 m), 2 m, 3 m, 4 m, 5 m, 6 m, 7 m, 9 m, 10 m, 12 m, and 6 y of child age.^{38,39} The PI has access to both datasets, and has 3 publications on infant nutrition, early childhood diet, growth, and obesity using Project Viva^{40,41} and IFPS II⁴² data since 2014. These two studies have a similar study design and complementary measures of child outcomes, which provide a unique opportunity for comprehensive analysis on the health effects of infant egg consumption and also external replication of findings.

Exposure measures (infant egg consumption). We will focus on age of introduction and frequency of intake as the key exposure measures of infant egg consumption, because evidence

Infant Egg Consumption | Child Health and Cognition | Clinical Guidelines

Figure 1. Conceptual framework on effects of infant egg consumption

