supports their potential influences on child health and development⁴³. We recognize that other aspects of infant egg consumption such as different egg fractions (i.e., white vs yolk⁴⁴) may also influence child outcomes but they were not collected in Project Viva or IFPS II.

Age of egg introduction. At **Project Viva** visits, the age of infant egg introduction was asked at 6-m and 12-m using the same question - “How old was your baby when you first fed him/her eggs”. In the **IFPS II**, mothers reported their infant’s intake of 18 types of foods in the past 7 days through monthly surveys from 2-12 m of infant ages. The question used for infant food intake was - “In the past 7 days, how often was your baby fed each food listed below? Include feedings by everyone who feeds the baby and include snacks and night-time feedings.” “Eggs” were one of the 18 types of foods. Accordingly, we will derive the infant age of egg introduction from IFPS II mothers’ monthly responses to infant egg consumption. Our previous analysis on infant dietary patterns showed that 1.7% and 63.0% of IFPS II infants had been introduced eggs by 6 m and 12 m of age, respectively⁴².

Frequency of egg intake. At the 2-y survey in **Project Viva**, the frequency of infant egg intake in the past month was obtained from the mothers’ response to the question - “Please check the box that best represents how often your child eats each of the foods listed, on average, in the past month”. One of the food items for this question was “Whole eggs”. Response options for the frequency of consuming “Whole eggs” included “never”, “<once/week”, “once/week”, “2–4 times/week”, “nearly daily or daily”, and “≥2 times/day”.

The same question was asked again at surveys at 3 y and 7 y. As mentioned above, mothers in the IFPS II reported their infant's intake of eggs in the past 7 days through the monthly surveys from 2-12 m of infant ages. Infant egg intake was reported as the number of feedings per day or per week. Our analysis on infant dietary patterns showed the mean egg intake among IFPS II infants was 0.01 (SD, 0.10) and 0.27 (SD, 0.37) serving/week at 6 m and 12 m, respectively⁴².

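### The printed IFPS II egg intake figures and the Aim 2 power claim need reconciling: as printed, at most 4.4% of infants reach 2 times/week, so the detectable odds ratio of 1.38 does not apply there, and the unit itself is doubtful

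*Combined protocol and SAP*

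**What the plan says.** The Statistical Power paragraph (section 3, Project Design) asserts sufficient power for both Aims on three grounds: cohort size, repeated outcome measurement, and that "infant egg consumption varied largely within cohorts". It gives detectable ORs of 1.46 (Project Viva, N=2,128) and 1.38 (IFPS II, N=3,033) at type 1 error 0.05 and power 0.8. Its one worked contrast belongs to Aim 1: introduction at 12 months or later versus 6-8 months. It gives no baseline risk, group shares, sidedness or Aim 2 contrast.

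Under Frequency of egg intake, in the same section, "the mean egg intake among IFPS II infants was 0.01 (SD, 0.10) and 0.27 (SD, 0.37) serving/week at 6 m and 12 m". Hypothesis 3 (section 2) predicts a non-linear association "with the optimal frequency being 2-4 times per week". For Aim 2 the Data analysis section uses six categories: "never, <once/week, once/week, 2–4 times/week, nearly daily or daily, and ≥ 2 times/day". In Project Viva, "the frequency of infant egg intake in the past month was obtained from the mothers’ response to the question" at the 2-year survey; the plan gives no distribution for that cohort.

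**The concern.** Two servings a week lies (2 - 0.27)/0.37 = 4.7 SDs above the printed 12-month IFPS II mean. Three of the six Aim 2 categories start at or above that level, and Hypothesis 3's optimum is one of them. If the printed figures are right, very few IFPS II infants fall there, and a detectable OR that fits a balanced split of the whole cohort says little about the contrast Hypothesis 3 turns on.

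At stake is whether IFPS II can replicate the Aim 2 findings at the predicted optimum, and whether a lowest-risk frequency of 2/week or more read from IFPS II would rest on data at that level or mainly on the shape of a curve fitted to lower intakes.

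**Working it through.** **Inputs.** N=3,033 and 2,128, OR 1.38 and 1.46, alpha 0.05, power 0.8 (Statistical Power). Mean 0.27, SD 0.37 at 12 months; mean 0.01, SD 0.10 at 6 months; 63.0% introduced to egg by 12 months (exposure measures). Baseline risk, split and sidedness are not stated and are assumed below.

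**1. Reproduce the plan's ORs.** Take a 10% comparison risk, equal halves and a two-sided 0.05 test (assumptions). The second risk is p2 = OR × p1/(1 - p1 + OR × p1). Power = Φ[(|p2 - p1| - 1.96 × s0)/s1], with s0 the pooled and s1 the unpooled standard error.

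- IFPS II: p2 = 0.138/1.038 = 0.1329; (0.0329 - 1.96 × 0.01165)/0.01163 = 0.87; power 0.81. The OR at 80% power is 1.376.
- Project Viva: p2 = 0.1396; (0.0396 - 1.96 × 0.01408)/0.01405 = 0.85; power 0.80. The OR at 80% power is 1.458.

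Both match the printed values, but not uniquely. A one-sided test with equal halves and about 7.5% risk also fits, as does a two-sided 25:75 split with about 13.5% risk.

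**2. Share of infants at 2/week or more.** Cantelli's inequality holds for any distribution: P(X ≥ 2) ≤ SD²/(SD² + (2 - mean)²).

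- 12 months: 0.1369/(0.1369 + 2.9929) = 0.0437, or about 133 of 3,033 (4.5% at worst rounding).
- 6 months: 0.0100/(0.0100 + 3.9601) = 0.0025.

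**3. Power for OR 1.38 with at most 133 infants.** This assumes no follow-up loss and pools all three upper categories. At 10% risk against the other 2,900:

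- Higher risk in the 133: (0.0329 - 1.96 × 0.02677)/0.02996 = -0.65; power 0.26.
- Lower risk in the 133 (p2 = 0.0745): (0.0255 - 1.96 × 0.02647)/0.02344 = -1.13; power 0.13. If instead the 133 have 10% risk and the others 13.3%, power is 0.17.

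The alternative reference group is the 37% not introduced by 12 months (0.37 × 3,033 = 1,122).

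| Comparison risk | Power, higher risk, vs 2,900 / vs 1,122 | Power, lower risk, vs 2,900 | Detectable OR (higher risk), vs 2,900 / vs 1,122 |
|---|---|---|---|
| 5% | 0.18 / 0.16 | 0.07 | 2.40 / 2.48 |
| 10% | 0.26 / 0.24 | 0.13 | 2.00 / 2.05 |
| 20% | 0.36 / 0.34 | 0.24 | 1.75 / 1.79 |

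Over risks from 2% to 50%, higher-risk power against all others runs from 12% to 44%.

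**4. Check the printed unit.** The plan says "Infant egg intake was reported as the number of feedings per day or per week", over the past 7 days. For a non-negative whole number X, X² ≥ X, so the variance is at least mean × (1 - mean) = 0.27 × 0.73 = 0.197 and the SD at least 0.444 (0.441 allowing for rounding of the mean). The printed SD is 0.37, so the figures cannot describe a whole-number count of feedings per week. The printed values also allow at most 0.1369/(0.1369 + 0.5329) = 20% of infants at 1/week or more at 12 months, against 63.0% ever introduced. These are different quantities, but the gap is wide.

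If the figures are per day (assumption), the weekly mean is 7 × 0.27 = 1.89 and the SD 7 × 0.37 = 2.59. The bound at 2/week is then 6.708/(6.708 + 0.0121) = 99.8%, which is no constraint. With 20-50% of infants at that level, an assumed range, power for OR 1.38 at 10% risk would be 64-81% for higher risk and 48-70% for lower risk.

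**The case against.** The strongest objection is that the fault may lie in the exposure section and not in the power claim. Step 4 supports this: the printed unit does not fit how intake was recorded, and on a per-day reading the mean is close to 2/week and the sparse-category argument falls away. This stands, and it makes every power figure in step 3 conditional. It does not remove the need to act, because no Aim 2 power is shown under either reading.

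A reader might infer that the statement about variation is simply false. The documents do not support that. The plan counts age of introduction as part of infant egg consumption, and "1.7% and 63.0% of IFPS II infants had been introduced eggs by 6 m and 12 m of age"; the statement also covers Project Viva.

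A reader might infer that Aim 2 as a whole is underpowered. That is not shown either. The bound concerns IFPS II infants, the six categories are Project Viva's own response options, and that cohort's distribution is not given.

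A reader might also infer that sparse intake is what stops IFPS II from testing Hypothesis 3. The hypothesis concerns an average over six outcomes, and the plan describes metabolic and cognitive measures for Project Viva only. IFPS II could not test the full composite even with ideal exposure variation; the loss is for the outcomes it does measure.

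Finally, the plan also fits fractional polynomials and restricts predictions to the observed intake range. A two-group test is therefore a proxy for the modelled analysis. The range restriction limits extrapolation but does not ensure adequate numbers at its upper end.

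**Conclusion.** The concern holds as an inconsistency to be reconciled, confined to IFPS II. Either the printed intake figures are wrong, or the 1.38 does not carry over to the 2-4 times/week level in that cohort.

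Taking the figures as printed, at most 4.4% of infants are at 2/week or more. At an assumed 10% risk and a two-sided 0.05 test, power for OR 1.38 is about 26% for higher risk in that group and about 13% for lower risk, the direction Hypothesis 3 predicts. The detectable OR for higher risk is about 2.0, or 1.75-2.5 over 5-20% risk and both reference groups. These figures use the largest possible exposed group and allow for no attrition, so they favour the plan. The 10% risk is back-solved and not unique, but no risk from 2% to 50% brings power near 80%.

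If the figures prove to be per day, the 4.4% bound disappears and the error is the unit. In both cases the plan lacks a power statement for any Aim 2 contrast.

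**What to change.** 1. Check the 0.27 (SD 0.37) figure and its unit against the IFPS II data, and correct the Frequency of egg intake paragraph if it is wrong.
2. Tabulate infants per Aim 2 category in each cohort.
3. In Statistical Power, limit 1.38 and 1.46 to the contrast and split for which they were computed. Add a separate detectable OR for 2-4 times/week versus its reference from the actual counts, with baseline risk, direction and sidedness stated.
4. If the weekly unit is confirmed, drop the variation argument as support for frequency power in IFPS II, collapse the IFPS II categories at 2/week and above into one, and do not read a lowest-risk frequency from that sparse range.

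The work is a frequency table per cohort, from data to which the investigator already has access, and rewording in the exposure, analysis and power paragraphs. The cost under the weekly unit is a less favourable detectable OR for Aim 2 and the loss of separate IFPS II estimates above 2/week.
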